PROTOCOL TITLE: Efficacy of a Coupler-Based Fitting Approach for Experienced Users Receiving Replacement Hearing Aids

PRINCIPAL INVESTIGATOR: [name], Au.D., Ph.D.

VERSION NUMBER AND DATE: Version 10, June 10, 2022

SPONSOR/FUNDING SOURCE: VA RR&D Merit Review C2777-R

Purpose

The overarching purpose of this project is to develop an accurate coupler-based fitting model for experienced hearing-aid users obtaining replacement hearing aids of any style that will result in positive patient outcomes while mitigating a face-to-face fitting visit.

The proposed project addresses three aims:

Specific Aim 1. Develop vent correction factors for testbox fittings of in-the-ear (ITE) and traditional behind the ear (BTE) with custom earmold hearing aids, which will be used to evaluate the real ear to complete difference (RECD)-fitting approach in a sample of experienced users receiving replacement hearing aids. Hypothesis 1a. RECD coupler-based fittings will accurately meet prescriptive targets and expected aided audibility for ITE and traditional BTE styles. Hypothesis 1b. Subjective outcomes from RECD coupler-based fittings will meet or exceed published norms.

Specific Aim 2. Develop correction factors for RECD coupler-based fittings of hearing aids with non-custom coupling (i.e., mini-BTEs with slim tubing and noncustom open canal coupling—open fits). Hypothesis 2. Correction factors will be developed to account for RECD coupler-based fittings with open canals.

Specific Aim 3. To determine if the open-fit RECD-fitting approach is equivalent to the standard of care (SoC) open-fit fitting approach. Hypothesis 3a. Derived REARs from open-fit RECD-fittings will accurately meet prescriptive targets and expected aided audibility and will be equivalent to in situ REARs in SoC fittings of open-fit styles. Hypothesis 3b. The subjective outcomes will not significantly differ between the experimental RECD-fitting group and the SoC group for open-fit styles.

Background and Significance

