In addition to the longer than desired wait time for the fitting appointment, Veterans and their family members also are inconvenienced with travel to the medical center. Many service-connected Veterans, however, are compensated for travel costs. Travel compensation costs for just the Mountain Home VA Medical Center last year (for all visits, not just audiology) totaled over \$8 million. Once the Veteran arrives at the medical center, s/he is often burdened with parking, navigating to the clinic, or finding a wheelchair or escort to facilitate navigation to the clinic. An efficacious RECD-based fitting approach that could bypass patient travel (and associated costs), a face-to-face appointment, and long wait-times for appointments would be highly desirable for many Veterans receiving replacement hearing aids and would have a significant impact on Veteran-Centric outcomes and VA resources. This project will evaluate an experimental coupler-based fitting procedures designed to greatly improve the efficiency of hearing-aid delivery to experienced hearing-aid wearers. Because the proposed model assumes that tubing length and earmold impressions (when applicable), as well as RECD measures are completed during the initial fitting, no visit is necessary for replacement hearing aid services.

Design

This project contains three separate experiments, one experiment for each aim.

Study 1 will use a quasi-experimental design. Two groups of experienced hearing aid users will receive replacement hearing aids using an experimental service-delivery approach. One group will be receiving replacement behind-the-ear (BTE) hearing aid style and the other group will be receiving replacement in-the-ear (ITS) hearing aids styles. The outcomes of the new hearing aids of both groups will be compared to the previous hearing aids and between groups.

Study 2 will use a quasi-experimental design. One group of subjects will receive 12 mini-BTE hearing-aid fittings (with both open and closed coupling) in one ear. The ears across subjects will be counter-balanced. Hearing aids from 3 different manufacturers and configurations will be fitted using a randomly assigned simulated audiogram. The output of these fittings will inform correction factors for hearing aid fitted in Study 3.

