Participants may directly benefit from this protocol. They all will receive a comprehensive audiologic evaluation and those results will be placed in their medical record. For those in Study 1 and 3, their current hearing aids will be evaluated to ensure proper function and best fit. If in need of repair, maintenance, or adjustment, these will be made. Their replacement hearing aids will be carefully fitted and verified to best practices and they will receive close follow-up regarding them. They may enjoy the benefit of obtaining hearing aids without having to come into the clinic for a face-to-face visit (experimental groups only). If the results between the SoC and experimental groups are equivalent, then this study would provide an evidence-based, RECD fitting approach that will improve Veteran-Centric care. Specifically, the RECD-based delivery model reduces the number of visits required to fit a replacement hearing aid compared to the SoC delivery model and, therefore, should result in greater patient satisfaction and reduced costs. In addition, the reduction in the number of clinic visits for established hearing aid patients may produce a reduction in wait times (greater access to care) for new patients seeking audiology services. The risks to participants is less than minimal and the anticipated benefits outweigh the minimal risk.

Selection of Subjects

Study 1 and Study 3: Inclusion Criteria:

Participants will be included in the study if the following criteria are met:

1. aged 18-85 years
2. experienced hearing-aid users who are obtaining replacement VA-issued hearing aids of the same style as their current hearing aids
3. competent hearing aid skills as demonstrated via the checklist (See appendix)
4. no more than a moderate sensorineural hearing loss (defined as less than or equal to 60 dB HL pure-tone average at 500, 1000, and 2000 Hz AU)
5. symmetrical hearing between the ears as defined as no more than a 20 dB difference in pure-tone thresholds at two consecutive frequencies
6. >/=50% word-recognition abilities in quiet as measured during the diagnostic audiologic evaluation

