Session 1 (Baseline, Pre-Fitting). All testing will be completed separately in each ear for both groups. Otoscopy will be performed. The standard audiometric evaluation including air- and bone-conduction pure-tone audiometry; word-recognition in quiet (NU-6 words) and in noise (Words-in-Noise test; Wilson et al., 2003; Wilson, 2003; Wilson and Burks, 2005) will be completed. Tympanometry and aural acoustic reflexes also will be measured. These results will be compared to the audiogram for the original fitting to rule out a significant change in hearing. The current hearing aids will be maintained and the fit will be verified via real-ear measurements. The Client Oriented Scale of Improvement (COSI) will be completed to obtain the listening goals of the participant and to facilitate programming needs of the replacement hearing aids (e.g., whether or not manual programs are needed/desired) along with outcome measures for their current hearing aids (presented in random order). Obtaining subjective outcomes from their current hearing aids will provide baseline scores for which to compare outcomes from the replacement hearing aids to ensure the outcomes from the replacement hearing aids are at least equivalent. In addition, an intake form (See Appendix) will be completed for both groups to determine other device options and function (e.g., volume control options such as yes/no or unlinked/linked; removal filament or not; earmold style from previous order form; etc. The participant will be asked to demonstrate hearing aid skills with their current hearing aids. If questions or concerns arise, then they will be re-oriented during this session or disqualified. Earmold impressions will be taken for replacement hearing aids. For the BTE group, only acrylic earmold material will be used.

For both groups, RECD values will be obtained separately for each ear with the foam insert following the ANSI S3.46 (2013) standard as implemented in Audioscan Verifit 2 system. In

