Study 1 Data Analysis Plan. A generalized linear model will be applied to examine fitting accuracy. This analysis will examine differences (in dB SPL) for in situ REAR (based on testbox fittings) across frequency between the groups relative to the prescription. Because it is expected that differences within the two ears of the same subject will be smaller than differences across subjects, inclusion of both ears in the same analysis may over inflate the statistical power. However, it is also of interest to ensure that all data are considered. Therefore, we propose to complete separate analyses for the left and right ear, even though we expect the pattern of results to be very similar for each ear. These analyses will determine (1) in situ REARs of the testbox fittings matched the prescription within each group, and (2) if there was an effect of fitting accuracy as a function of style. A generalized linear model will be conducted to compare the expected (from prescription) and actual aided SII within and between groups. Finally, separate mixed model repeated measures ANOVA will be applied to examine group differences among the outcome measure subscales (i.e., SADL subscales, IOI-HA items/subscales, and for the APHAB subscales) to examine differences in outcomes between groups and between current hearing aid fittings and the replacement testbox fittings. For the COSI, the percentage of 'better' and 'much better' responses and the average of the final ability will be calculated across goals and compared between groups via a paired-sample t-test. The subjective outcomes of replacement hearing aids (Session 3) from testbox fittings will also be compared to normative data for each group by comparing our mean, standard deviation, and sample size to those same variables from the published outcome respectively via a Welch test. This will inform whether our outcomes for testbox fittings of replacement hearing aids from each group were consistent with the published norms or not. For the IOI-HA, the IOI-HA norms from the VA ROES DALC database that contains over 100,000 IOI-HA records will be used. In the same fashion, we can select IOI-HA norms from ROES by based on degree of hearing loss and hearing aid style. A

logistic regression also will be conducted to examine if the proportion of responses differ between the groups on the specific telephone and exit survey items of interest.

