Study 3 Data Analysis. We will use a similar data analysis plan as in Study 1 for real ear/fitting accuracy variables. This will determine if derived REARs from open-fit RECD-fittings will accurately meet prescriptive targets and expected aided audibility and if *in situ* REARs of RECD-fittings are equivalent to *in situ* REARs in SoC fittings of open-fit styles. For statistical reasons, we propose to complete separate analyses for the left and right REAR data as described in Experiment 1. For self-report data, a separate mixed model repeated measures ANOVA will be conducted to compare outcomes amongst the groups. This will determine if subjective self-report outcomes across a variety of domains differs as a function of fitting experience and open-fit style.

The data will be analyzed by the PI; her collaborator and co-investigator ([name]., at Vanderbilt University—coded data only) who also will develop the correction factors; and the statistical consultant at Duke University (to be determined). A copy of coded data only will be

stored on the Duke University Server. A copy of all electronic data will also be stored at VA on \\v06.med.va.gov\\dur\\Research\\Research\\[name].

Privacy, Confidentiality, and Information Security

1. Lists of Data Reviewed and/or Collected for Screening/Recruitment and Conduction of Study:

It will be obtained, used, and/or shared for this study includes:

Identifier(s)	Source(s) of Health Information
 Names	 Medical history & physical exam information
 All geographic subdivisions smaller than a State, including street address, city, county, precinct, and zip code. Describe: mailing address	 Photographs, videotapes, audiotapes, or digital or other images
 All elements of dates (except year) for dates directly related to an individual, including birth date, admission date, discharge date, visit or treatment dates, etc.; and all ages over 89, Describe: age, audiology treatment dates (hearing test dates, fitting dates)	 Biologic specimens (e.g., blood, tissue, urine, saliva). Describe:
 Telephone numbers	 Progress notes
 Fax numbers	 Diagnostic / Laboratory test results

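### For the self-report scales, a group main effect averaged over old-aid and new-aid scores would not test whether the new aids' outcomes differ between groups; the plan should name the contrast that does

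*Combined protocol and SAP*

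**What the plan says.** The Design section sets the Study 1 question: "The outcomes of the new hearing aids of both groups will be compared to the previous hearing aids and between groups". Under Study Interventions, Study 1, Session 1, the scores on the old aids are described as a baseline: "Obtaining subjective outcomes from their current hearing aids will provide baseline scores for which to compare outcomes from the replacement hearing aids". The Study 1 Data Analysis Plan then says that "separate mixed model repeated measures ANOVA will be applied to examine group differences among the outcome measure subscales", with the purpose "to examine differences in outcomes between groups and between current hearing aid fittings and the replacement testbox fittings". So both fittings enter the model. For these three instruments the plan names no group-by-session term, no Session 3 contrast and no adjustment for the Session 1 score. Session 3 scores stand alone only in the Welch comparison with published norms, which is made within each group.

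Two features of Study 1 matter here. On allocation: "Study 1 will use a quasi-experimental design", with groups defined by hearing-aid style. Under Selection of Subjects, participants are those "obtaining replacement VA-issued hearing aids of the same style as their current hearing aids".

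For Study 3, the Data Analysis paragraph says that "a separate mixed model repeated measures ANOVA will be conducted to compare outcomes amongst the groups". It does not name the repeated factor. Hypothesis 3b reads: "The subjective outcomes will not significantly differ between the experimental RECD-fitting group and the SoC group for open-fit styles".

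**The concern.** The Design section asks about the new aids. The two comparisons named in the analysis plan correspond to the two main effects of a group-by-session model, and the group main effect in such a model pools each person's old-aid and new-aid scores. Used as the answer to the between-group question, it has two faults. A real difference on the new aids is diluted by a score taken before the new aids were fitted. And a difference that existed only on the old aids can produce a significant group effect.

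The second fault is a practical risk in Study 1. The BTE and ITE groups are not randomised and each person keeps the same style, so the groups may well differ before fitting. In Study 3, if session is in the model, the first fault would matter for Hypothesis 3b, because that hypothesis is worded as an absence of significant difference and dilution makes non-significance more likely.

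**Working it through.** **Plan's own figure.** There is none to reproduce for this analysis. The Study 1 power calculation (50 participants over two groups, alpha 0.05) concerns fitting accuracy. I take only the group size from it: 50/2 = 25 per group.

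**Assumptions not in the documents.** A difference of 0.5 SD, present at one session only; unit SD at each session; old-new correlation rho of 0.3, 0.5 or 0.7.

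**What each test targets.** Let D_old and D_new be the group differences at Sessions 1 and 3.
- Group main effect: equivalent to a two-sample t test on each person's two-session mean. It estimates (D_old + D_new)/2, with SD sqrt((1 + rho)/2). Its null is D_old + D_new = 0. In simulation, the ANOVA F and the squared t on the means agreed to about 1e-14.
- Session 3 contrast: estimates D_new, SD 1.
- Group-by-session term: estimates D_new − D_old, SD of change sqrt(2(1 − rho)).
- Session 3 adjusted for Session 1: estimates D_new − rho × D_old, residual SD sqrt(1 − rho²).

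Power follows from the noncentral t with noncentrality = difference / (SD × sqrt(2/n)). With n = 25, sqrt(2/25) = 0.283.

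**Groups equal on old aids, 0.5 SD apart on new aids, 25 per group**

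| Test | Estimate | SD at rho 0.3 / 0.5 / 0.7 | Noncentrality | Power |
|---|---|---|---|---|
| Group main effect | 0.25 | 0.806 / 0.866 / 0.922 | 1.10 / 1.02 / 0.96 | 0.19 / 0.17 / 0.16 |
| Session 3 contrast | 0.50 | 1 | 1.77 | 0.41 |
| Group-by-session | 0.50 | 1.183 / 1.000 / 0.775 | 1.49 / 1.77 / 2.28 | 0.31 / 0.41 / 0.61 |
| Session 3 adjusted | 0.50 | 0.954 / 0.866 / 0.714 | 1.85 / 2.04 / 2.48 | 0.44 / 0.52 / 0.68 |

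**Groups 0.5 SD apart on old aids, equal on new aids.** The main effect again estimates 0.25, so by symmetry it rejects 16% to 19% of the time. A Session 3 contrast rejects 5%.

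**Groups 0.5 SD apart at both sessions.** The unadjusted Session 3 contrast rejects 41% of the time, although the difference predates the fitting. The group-by-session term rejects 5%. The adjusted contrast estimates 0.5 × (1 − rho) = 0.35 / 0.25 / 0.15, so adjustment shrinks a persisting style difference but does not remove it.

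**Check with the plan's effect size.** Eta-squared 0.10, given for fitting accuracy, implies f = sqrt(0.10/0.90) = 0.333 and d = 2f = 0.667. With 25 per group and a new-aid difference only, power is 0.30 / 0.27 / 0.24 for the main effect, 0.64 for the Session 3 contrast and about 0.68 / 0.76 / 0.90 with baseline adjustment. In 20,000 simulated trials at rho 0.5, the main effect returned 0.332 for a true new-aid difference of 0.667. With an old-aid difference only, it rejected 26.8% of the time, against 5.3% for the Session 3 contrast.

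**Study 3, only if session is a repeated factor.** The plan has 76 participants before attrition, 19 per group. For EXP against SoC pooled over domes (2 × 19 = 38 per arm) and 0.5 SD on the new aids only, power is 0.22 to 0.27 for the main effect against 0.58 for a Session 3 contrast. For open domes alone (19 against 19) it is 0.13 to 0.15 against 0.32.

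**The case against.** The strongest reply is that the plan names no test rather than the wrong one. Its two phrases may simply list the factors of the model; the same ANOVA yields the group-by-session term and the simple effects, and nothing says the main effect decides. That stands. A reader might infer that the plan commits itself to the session-averaged test, but the text does not go that far. What remains is that tests with different nulls are left open, and the literal reading points to the least suitable one.

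For Study 3, a reader might infer that Hypothesis 3b is already tilted towards a null result. The documents do not support this. The stated aim there is to see whether outcomes across several domains differ by fitting experience and open-fit style, so subscale could be the repeated factor. If only Session 3 scores enter, there is no dilution.

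It can also be said that the BTE-ITE self-report comparison tests no numbered hypothesis. Hypothesis 1b is judged against norms using Session 3 scores, and the COSI and survey items have their own analyses. That is correct and limits the reach of the point. So does the fact that exact halving needs equal groups on the old aids, and that the one-session-only scenarios are assumed ones; given same-style replacement, a difference at both sessions is at least as plausible.

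Finally, an unadjusted Session 3 contrast would not cure Study 1, since it would still report a persisting style difference. That is why the remedy is baseline adjustment together with the group-by-session term.

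**Conclusion.** The point holds conditionally. If the group main effect is used for the between-group conclusion on SADL, IOI-HA or APHAB, it answers a different question from the one in the Design section. Under the assumed 0.5 SD difference at one session and correlation of 0.3 to 0.7, with 25 per group, its power is less than half that of a Session 3 contrast (0.16 to 0.19 against 0.41), and baseline adjustment does better still (0.44 to 0.68). It would also reject 16% to 19% of the time for a difference confined to the old aids. The direction follows from the algebra; the sizes depend on the assumptions.

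It does not follow that the plan has chosen this test, nor that Study 3 is affected; the latter turns on whether session is a repeated factor. These scales are not the primary outcome, so the sample sizes and the fitting-accuracy analysis stand. The scales do bear directly on Hypothesis 3b, so the deciding contrast should be fixed in advance.

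**What to change.** In the Study 1 Data Analysis Plan and the Study 3 Data Analysis paragraph:

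1. Base the between-group conclusion for each self-report scale on the Session 3 group difference, adjusted for the Session 1 score on the same scale, reported with a 95% CI.
2. In Study 1, also report the group-by-session term as the difference in change, and state that a style difference already present at Session 1 will not be attributed to the testbox fitting.
3. State that the group main effect averaged over sessions will decide neither the Study 1 style comparison nor Hypothesis 3b.
4. State what the repeated factor is in the Study 3 self-report model.

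The Session 1 scores are already collected in both studies. The cost is a few sentences of analysis wording, with no new data, visits or participants.

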Study 1 Power Analysis. The primary outcome of interest is based on fitting accuracy of each ear (i.e., deviation of REAR from prescriptive target across frequency). A power analysis for a repeated measure ANOVA with an effect size $\eta^2 = 0.10$, power ($1-\beta$) = 0.80, and $\alpha = 0.05$ requires a sample size of 100 ears (total of 50 participants) over the two groups. A small effect size is expected, as a small effect size was found in the preliminary data ($\eta^2 = 0.10$). Considering 15% attrition, then 8 additional participants will be needed ($N = 58$) resulting in 29 participants per group.

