 Electronic mail addresses	 Operative reports
 Social Security Numbers	 Imaging (x-ray, CT, MRI, etc.)
 Medical record numbers	 Discharge summaries
 Health plan beneficiary numbers	 Survey / Questionnaire responses
 Account numbers	 Billing records
 Certificate and/or license numbers	 HIV testing or infection records
 Vehicle identifiers and serial numbers, including license plate numbers	 Sickle cell anemia information
 Device identifiers and serial numbers	 Alcoholism or alcohol use information
 Web Universal Resource Locators (URLs)	 Drug abuse information
 Internet Protocol (IP) address numbers	 Mental health (not psychotherapy) notes
 Biometric identifiers, including finger & voice prints	 Psychological test results
 Full-face photographic images and any comparable images	 Genetic testing
 Any other unique identifying number, linked study ID, characteristic, or code, describe: each substudy will have a unique study ID based on group assignment and number of subject entering the study. For example, Study 1: ITE01, BTE 01	 Other, describe:

2. Data and/or Specimen Acquisition:

Data for this study will be collected through (*check all that apply*):

- Prospective data and/or specimen collection obtained from participants. Provide description of processes: The prospective data will be collected from participants as described above for Study 1, Study 2, and Study 3.

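### Study 1 compares COSI scores between two separate groups of people with a paired t-test, so the p-value depends on arbitrary row order

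*Combined protocol and SAP*

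**What the plan says.** The Study 1 Data Analysis Plan derives two COSI summaries: the percentage of goals rated in the top two improvement categories, and the mean final ability. The second, like the first, is treated as follows: "the average of the final ability will be calculated across goals and compared between groups via a paired-sample t-test". No other test of the COSI between the Study 1 groups is given.

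The groups are defined in the Design section: "One group will be receiving replacement behind-the-ear (BTE) hearing aid style and the other group will be receiving replacement in-the-ear (ITS) hearing aids styles". Selection of Subjects requires that participants be "obtaining replacement VA-issued hearing aids of the same style as their current hearing aids", so a person belongs to one style only. The privacy section gives each substudy a "unique study ID based on group assignment and number of subject entering the study", with separate ITE and BTE number series as the example. The Study 1 Power Analysis plans 50 analysable participants over the two groups and allows for 15% attrition, "resulting in 29 participants per group".

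**The concern.** A paired t-test analyses differences within linked pairs. It is valid when each observation in one column has a natural partner in the other, such as the same person measured twice or a matched pair. A BTE user and an ITE user in this study have no such link. Run as written, the test would pair people by position in the data file, drop anyone without a partner, and halve the degrees of freedom.

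At stake is the inference on one of the four subjective outcome measures taken at Session 3 (COSI, APHAB, IOI-HA, SADL). Two analysts with the same data in different row orders could both follow the plan and reach different conclusions.

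**Working it through.** **Inputs from the document.**
- Study 1 Power Analysis: 50 analysable participants over two groups, so 25 per group; 29 per group enrolled; 15% attrition; alpha 0.05. That alpha is stated for fitting accuracy, and I take it as two-sided.
- The plan gives no SD, effect size or sample size for the COSI, so there is no figure of its own to reproduce.

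**Assumptions.** Approximately normal scores, equal SDs, and a true difference of 0.5 to 0.8 SD.

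**Step 1: is there any pairing?** I looked for four possible links.
- Same person in both groups: excluded by the same-style criterion.
- Matched recruitment: the Design section describes two groups and no matching.
- Study ID: numbers follow order of entry within each group, so equal numbers share only a position in the queue.
- Goals: at Session 1, "The Client Oriented Scale of Improvement (COSI) will be completed to obtain the listening goals of the participant". Goals are personal to each participant and do not pair across people.

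None supplies a pair.

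**Step 2: what the test does without pairs.** With equal SDs s and n per group:

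- independent t = difference / (s × √(2/n)), with 2n − 2 degrees of freedom
- paired t = difference / (s × √((2 − 2r)/n)) = independent t / √(1 − r), with n − 1 degrees of freedom

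Here r is the sample correlation between the two columns as they are lined up. With unrelated people r is pure noise, set by row order, with SD about 1/√(n − 1). At n = 25 this is 1/√24 = 0.204.

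**Step 3: numbers at n = 25 and an observed difference of 0.5 SD.**
- Independent t = 0.5/√(2/25) = 1.768 on 48 df, p = 0.083.
- r = +0.4 (about 2 SD): paired t = 1.768/√0.6 = 2.282 on 24 df, p = 0.032.
- r = −0.4: paired t = 1.768/√1.4 = 1.494 on 24 df, p = 0.148.
- Critical t is 2.064 on 24 df, against 2.011 on 48 df. The paired test is significant when r exceeds 1 − (1.768/2.064)² = 0.266, which chance alone gives in about 10% of orders.

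**Step 4: direct check.** Two fixed samples were re-paired at random 20,000 times.

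| n per group | Independent p (fixed) | Paired p, full range | Paired p, central 95% | Orders with p < 0.05 |
|---|---|---|---|---|
| 25 | 0.083 | 0.007 to 0.194 | 0.033 to 0.151 | 9.5% |
| 29 | 0.062 | 0.002 to 0.150 | 0.023 to 0.115 | 24.5% |

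This agrees with Step 3. Order need not be random, either. At n = 25, sorting both columns in the same direction gives p = 0.000003, and sorting them in opposite directions gives p = 0.22.

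**Step 5: how often the verdict changes (25 per group, assumed 0.667 SD).** In 37% of 1,000 simulated data sets, at least one of 200 orders gave a different verdict at 0.05 from the others. A single random order disagrees with the Welch test in about 6% of data sets, and two random orders disagree with each other in about 9%. With no true difference these shares are about 2% and 3%.

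**Step 6: average behaviour when order is unrelated to outcome (25 per group).** Type I error is 5.1% for both tests. Power, paired against independent:
- 0.5 SD: 39.7% v 40.9%
- 0.667 SD: 62.1% v 63.9%
- 0.8 SD: 77.3% v 79.0%

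**Step 7: unequal groups.** If each of 29 participants per group completes independently with probability 0.85, the chance that the two completer counts differ is one minus the sum of the squared binomial probabilities, about 85%. The paired test then cannot be computed without dropping someone.

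**The case against.** The strongest reply is that little is lost in practice. Type I error is nominal when order is unrelated to outcome, the power loss is under 2 points, and the critical value barely moves. The 37% figure depends on the number of shuffles: it was 27% with 20 and 45% with 1,000. An analyst uses one order, for which about 6% is the relevant figure. The effect sizes are assumed. The primary outcome is fitting accuracy, and Hypothesis 1b concerns published norms, which the plan tests separately with a Welch test. All of this stands and limits the severity. It does not make the test valid: the p-value for a given data set is still arbitrary. It can be repeated from the same ordered file, but not from the data alone.

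A second reply is that a within-person comparison of current and replacement aids was meant. The preceding sentence makes that contrast for the SADL, IOI-HA and APHAB, and Study 3 lists the COSI in its battery on the current aids. But the COSI sentence says the comparison is between groups. In Study 1 the Session 1 COSI is described as setting goals and guiding programming, and COSI outcomes are measured at Session 3. If the within-person contrast was intended, the sentence still needs rewording.

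On unequal groups, recruitment continues until the target of usable data is reached, which could restore balance. However, that target is a Study 1 total and not a number per style.

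**Conclusion.** The concern holds. As written, the test does not fit the comparison: the groups are unmatched individuals, so the standard error and p-value depend on file order. In the illustration at 25 per group, p ranged from 0.007 to 0.194 against a fixed 0.083. Those particular values rest on an assumed 0.5 SD difference and normal scores. The dependence on order needs neither assumption.

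This should be corrected before analysis. It is not a threat to the study's main conclusion, because it touches a secondary comparison and causes no systematic inflation of error when row order is unrelated to outcome.

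**What to change.** In the Study 1 Data Analysis Plan, replace the paired test with an independent-samples (Welch) t-test of BTE against ITE. Apply it to two values per participant: the percentage of that person's goals rated better or much better, and that person's mean final ability. Say explicitly that these are computed within participant before the groups are compared.

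Keep paired tests for within-participant contrasts. If the authors also want COSI compared between current and replacement aids, add this as a separate sentence and state which Session 1 COSI score serves as the baseline.

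The cost is one phrase. The plan already uses a Welch test for its comparisons with norms, no extra data are needed, and the test handles unequal groups without dropping anyone.
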